## 1. STUDY DETAILS

### 1.1 Study Objectives

#### 1.1.1 Primary Objective

The primary objective is to compare the mean change from baseline in HbA1c between dapagliflozin 10 mg and placebo, after 24 weeks of oral administration of double-blind treatment in patients with type 2 diabetes who have inadequate glycemic control, defined as HbA1c  $\geq 7.0\%$  but  $\leq 11\%$  at Visit 1, and CKD stage 3A (eGFR 45 to 59 mL/min/1.73 m^2, inclusive, at Visit 1, or Visit 2, or Visit 3 and eGFR 40 to 65 mL/min/1.73 m^2, inclusive, at Visit 1).

#### 1.1.2 Secondary Objectives

The secondary objectives are to compare dapagliflozin 10 mg and placebo after 24 weeks (or prior to rescue) of oral administration of double-blind therapy for the following:

- The percent change from baseline in total body weight at Week 24
- The change from baseline in FPG at Week 24
- The change from baseline in seated SBP at Week 24

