2.2 Secondary objectives

Secondary Objective:	Outcome Measure :
To compare the percent change from baseline in total body weight between dapagliflozin 10 mg and placebo, after 24 weeks of oral administration of double-blind treatment.	Percent change from baseline in total body weight at Week 24

¹ Summary of the algorithm for inclusion based on HbA1c and eGFR:

Sample obtained at Visit 1: HbA1c $\geq 7.0\%$ and $\leq 11\%$
eGFR 40-65 mL/min/1.73 m², MDRD-formula
Samples obtained at Visit 1, or Visit 2, or Visit 3: eGFR 45-59 mL/min/1.73 m², MDRD-formula

To compare the change from baseline in FPG between dapagliflozin 10 mg and placebo, after 24 weeks of oral administration of double-blind treatment.	Change from baseline in FPG at Week 24
To compare the change from baseline in seated SBP between dapagliflozin 10 mg and placebo, after 24 weeks of oral administration of double-blind treatment.	Change from baseline in seated SBP at Week 24

[figure not shown]

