#### 4.1.3 Derivation of Efficacy Variable at Rescue/ Premature Discontinuation

In efficacy analyses, the glycemic parameters will only include measurements obtained prior to or on the date of rescue medication administration or discontinuation of double-blind medication (whichever is earlier). An exception would be in sensitivity analysis, where the analysis is performed on data regardless of rescue (see more details in Section 4.2.6.2).

For secondary efficacy variables of body weight (kg), seated SBP (mmHg) and remaining exploratory variables, measurements after rescue medication will not be excluded from the analyses.

Patients not completing the treatment period should have all Week 24 visit procedures done at the time of study discontinuation or rescue.

Patients who meet the pre-specified rescue criteria, at the specified visit described in Table 4, will be scheduled for a follow-up visit (within 3-5 days) to obtain a confirmatory central lab FPG value. If the confirmatory FPG value still meets the criteria, the patient will be rescued.

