**Table 11 Summary of Analyses to Meet Secondary Efficacy Objectives**

Analysis type	LOCF or Observed values	Analysis set
Repeated measures mixed model of percent change from baseline to Week 24 in body weight (kg) (prior to treatment discontinuation)	Observed values	FAS
Repeated measures mixed model of change from baseline to Week 24 in FPG (mg/dL (prior to rescue and treatment discontinuation)	Observed values	FAS
Repeated measures mixed model of change from baseline to Week 24 in seated SBP (mmHg) (prior to treatment discontinuation)	Observed values	FAS

LOCF = Last Observation carried Forward; FAS = Full analysis set

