### **4.3 Conventions**

#### **4.3.1 Visit and Period Windows**

Patients do not always adhere strictly to the visit timing in the protocol. Therefore the designation of visits during the double-blind treatment period and follow-up period will be based on the day of evaluation relative to the reference start date rather than the nominal visit recorded in the CRF.

To assign a measurement to a Week t during a study period, the first step consists of selecting all measurements falling within this study period as defined below. To further determine the Week t measurement, mutually exclusive relative day windows are used.

The day windows are defined to provide derived visits that correspond to the post-baseline time points specified in the protocol. As already stated, some restrictions may exist on some laboratory assessments to be included in efficacy analyses. These restrictions will be reflected in the day ranges. For example, since no HbA1c is to be collected at Week 1, the windows for HbA1c will only start at Week 4. No Week 1 windowing will be defined.

For each visit, a window will be defined such that the lower and upper bounds of each window is generally the midpoint between 2 consecutive study visits. The visit windows and applicable study day ranges are presented below in [Table 17](#).

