#### 4.3.2 Post-Dosing Efficacy Observations

While double blind treatment period efficacy observations will be listed regardless of whether the patient was taking blinded study drug. Observations will be included in summarizes of the FAS only if the following rules are satisfied:

- HbA1c, body weight, BMI and CCI will be summarized only if measured on or before the 8th day after the last double-blind drug dosing date.
- FPG, CCI SBP, eGFR and Insulin initiation will be summarized only if measured on or before the 1st day after the last randomized, double-blind drug dose date.
- Lipids and other exploratory parameters (if available) will be summarized only if measured on or before the 4th day after the last randomized, double-blind drug dose date.
- The efficacy measurements of HbA1c and FPG will be summarized/analysed only if measured on or prior to the first dose of rescue medication.

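### Does the rescue wording in SAP 1.1.2 leave it unclear whether post-rescue body weight and seated SBP are analysed?

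*SAP*

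**What the plan says.** SAP 1.1.2 places percent change in body weight, change in FPG and change in seated SBP under a single stem, "after 24 weeks (or prior to rescue) of oral administration of double-blind therapy".

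The analysis sections separate the three endpoints. SAP 4.1.3 stops glycemic parameters at rescue or at discontinuation of double-blind drug, whichever is earlier. For body weight, seated SBP and the remaining exploratory variables it says that "measurements after rescue medication will not be excluded from the analyses". Table 11 gives the rule row by row:

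- weight: "Repeated measures mixed model of percent change from baseline to Week 24 in body weight (kg) (prior to treatment discontinuation";
- SBP: "Repeated measures mixed model of change from baseline to Week 24 in seated SBP (mmHg) (prior to treatment discontinuation";
- FPG alone: "prior to rescue and treatment discontinuation".

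SAP 4.3.2 adds limits on days since last dose for each variable and then a rescue limit for two of them: "The efficacy measurements of HbA1c and FPG will be summarized/analysed only if measured on or prior to the first dose of rescue medication".

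The protocol's weight objective (Section 2.2) reads, in part, "percent change from baseline in total body weight between dapagliflozin 10 mg and placebo, after 24 weeks of oral administration of double-blind treatment"; the SBP objective is parallel. Neither mentions rescue. Protocol 8.5 sets pre-rescue data as the default for efficacy endpoints but allows exceptions, and Protocol 8.1 refers to the SAP for detail.

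**The concern.** Read literally, the SAP states one objective and plans a different analysis for two endpoints that are tested formally. Rescued patients stay on blinded drug and keep their visit schedule, so on-treatment values after rescue will exist, and the rule decides whether they count.

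Weight is tested first after HbA1c. If it fails, FPG and SBP are not formally tested. If rescue agents themselves shift weight or blood pressure, the estimate could depend on which rule is followed. A dispute after unblinding about which rule had been pre-specified would be awkward.

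Two other texts seem to support the 1.1.2 wording: the pre-rescue default in Protocol 8.5, and SAP 4.2.6.3, which describes the secondary model as similar to the primary one. The primary analysis drops post-rescue data.

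**Working it through.** **1. Is a planned figure involved?** No. The nearest is the sample size, which uses HbA1c inputs only (SAP 1.4: difference 0.3, SD 0.9, two-sided 0.05, 80% power). Per group, n = 2 × (1.960 + 0.842)² × 0.9² / 0.3² = 2 × 7.85 × 9 = 141.3, so 142 by the normal approximation. The two-sample t-test gives 142.2, so 143. Then 143 / 0.95 = 150.5, so 151 per group and 302 in total, as planned. Nothing about weight, SBP or rescue enters.

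**2. The statements side by side.**

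| Place | Body weight | FPG | Seated SBP |
|---|---|---|---|
| Protocol 2.2 (objective) | no rescue limit | no rescue limit | no rescue limit |
| SAP 1.1.2 (objective) | rescue mentioned | rescue mentioned | rescue mentioned |
| SAP 4.1.3 (data rule) | post-rescue kept | cut at rescue | post-rescue kept |
| SAP Table 11 (analysis) | cut at discontinuation | cut at rescue and discontinuation | cut at discontinuation |
| SAP 4.3.2 (inclusion limits) | to 8th day after last dose; no rescue limit | to 1st day after last dose; rescue limit | to 1st day after last dose; no rescue limit |

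For weight and SBP, only SAP 1.1.2 stands apart. The three analysis-level rows agree.

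**3. Would the two readings use different data?** They could. SAP 4.3.1 assigns visits "based on the day of evaluation relative to the reference start date rather than the nominal visit recorded in the CRF", and Table 17 opens the Week 24 window for weight and vital signs on Day 128. FPG is assessed for rescue at Visit 6 (Day 29 ± 5) and Visit 7 (Day 85 ± 5), with a repeat sample 3 to 5 days later:

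- Visit 6: 29 − 5 + 3 = Day 27, to 29 + 5 + 5 = Day 39.
- Visit 7: 85 − 5 + 3 = Day 83, to 85 + 5 + 5 = Day 95.
- Days left before the Week 24 window: 127 − 95 = 32.

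A patient rescued from a scheduled FPG, with rescue started within those 32 days, has the early Week 24 procedures assigned to an earlier window. If post-rescue values were dropped, that patient would have no Week 24 weight or SBP and the mixed model would rely on missing at random. Under SAP 4.1.3 the value nearest Day 169 is used if the patient is still on drug and attending.

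This contrast needs 1.1.2 to be read as an exclusion rule for the mixed model, which it does not say. It could equally mean that the last value before rescue stands in for Week 24, as SAP 4.1.5 does for glycemic parameters under last observation carried forward. Table 11 specifies observed values for all three endpoints, so carrying forward is not the planned analysis either.

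**4. Can the effect be sized?** No. The documents give no rescue rate, no effect of rescue on weight or SBP, and no SD for either. Counting calendar days on which rescue could occur does not help. Days are not patients, and the Week 4 start applies to the FPG criteria only. Protocol 4.3.3.1 also treats a sustained insulin increase as rescue during the double-blind period, with no Week 4 start.

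**5. Which rule does the analyst follow?** SAP 4.2.6.4 takes the testing order from Table 11, where each endpoint's data cut is stated beside it. The tested analysis and its data rule are therefore read from the same table row.

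**The case for a change.** The strongest case for acting is that these are confirmatory endpoints and the text is current. The Protocol 8.5 default points to pre-rescue data, the readable part of Protocol 8.5.2 names no exception for weight or SBP, and SAP Section 6 declares no changes from the protocol. In the visible text, sensitivity analyses cover the primary endpoint only, so a reader could not see whether the weight or SBP result depends on the rescue rule. Correcting one parenthesis and adding two supportive models would cost little.

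Part of this stands: the mismatch is real, and the wording of 1.1.2 is wrong for two of three endpoints. The rest does not carry. The Protocol 8.5 default gives way where something else is specified, and SAP 4.1.3 specifies it by endpoint name. Part of Protocol 8.5.2 is redacted, as are much of the SAP's exploratory section and its tables, so the absence of an exception or of further analyses cannot be inferred. A similar model in SAP 4.2.6.3 refers to the form of the model; Table 11, in the same section, states the data cut. A pre-rescue model for weight and SBP would be a reasonable optional extra, but it would repair no error and would not enter the testing sequence.

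**Conclusion.** No change follows. This is a clerical slip in an introductory objectives sentence. The plan as written leads to one identifiable and sound analysis: weight and seated SBP include post-rescue values up to discontinuation of double-blind drug, within the post-dose limits of SAP 4.3.2, while FPG stops at rescue. Confining the parenthesis in 1.1.2 to FPG would be harmless tidying if the SAP were reopened for another reason, but it would alter no dataset, model or test.

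The effect on sample size, type I error and testing order is nil. The effect that a different rescue rule would have on the weight or SBP estimate cannot be derived from the documents. The conclusion assumes that analysts work from SAP 4.1.3, Table 11 and 4.3.2 rather than from the objectives sentence, and that no redacted text contradicts those three.

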### 1.1.3 Safety Objective

The safety objectives include:

- To examine eGFR changes during the study and 3-week post-treatment for dapagliflozin 10 mg and placebo.
- To assess the proportion of patients discontinued from study medication because of worsening renal insufficiency (defined as patients reaching confirmed eGFR levels  $<30 \text{ mL/min/1.73 m}^2$ ) between dapagliflozin 10 mg and placebo.
- To evaluate the safety and tolerability of dapagliflozin 10 mg once daily in type 2 diabetes and CKD stage 3A.

### 1.1.4 Exploratory Objectives

Exploratory objectives aim to investigate the treatment difference between dapagliflozin compared with placebo when added to current background therapy in patients with T2DM and CKD3A, for the parameters listed in [Table 1](#).

**Table 1 Exploratory objectives and outcome measures**

Exploratory Objective:	Outcome Measure :
CCI	

**Table 1                    Exploratory objectives and outcome measures**

Exploratory Objective:	Outcome Measure :
 CCI	

**Table 1                      Exploratory objectives and outcome measures**

Exploratory Objective:	Outcome Measure :
 CCI	

**Table 1                      Exploratory objectives and outcome measures**

Exploratory Objective:	Outcome Measure :
	

**1.1.5      Adjudication cases summarization**

Pre-defined liver enzyme elevations will undergo adjudication. Adjudicated results will be summarized by treatment group. Liver abnormalities submitted for review by the hepatic adjudication committee will be listed.

All potential events of DKA will be recorded in the eCRF and submitted to an independent DKA Adjudication Committee. Adjudicated results will be summarized by treatment group. DKA events submitted for review by the DKA adjudication committee will be listed.

[figure not shown]
**1.2              Study Design**

This is a confirmatory, phase III, randomized, double-blind, 2-arm, parallel group, placebo-controlled, multi-national, multi-centre study to evaluate the clinical efficacy and safety of dapagliflozin in patients with type 2 diabetes and CKD stage 3A.

The study consists of 2-week screening period, a 4-week single-blind placebo lead-in period, a 24-week double-blind placebo-controlled treatment period, and a 3-week follow-up period. Patients will be randomized to 24 weeks treatment with dapagliflozin 10 mg or matching placebo after the placebo lead-in period. Figure 1 illustrates details on timing of visits. Table 2 provides details on schedule of study procedures.

The study will be an international multi-centre study at approximately 100 centres from countries across North America and European regions.

**Figure 1 Study flow chart**

R = Randomization, DB = Double-blind, V = Visit, Wk = Week

**Table 2 Study Plan detailing the procedures**

Study Period	Screening period		Lead-in period		Treatment period				Follow-up period
	Enrolment	Start of lead-in	Lead-in	Randomization	Treatment	Treatment	Treatment	End of Treatment/Discontinuation/Rescue	Follow-up
Visit									
Visit Number (Fasting/Non-fasting)	1 a Non-fasting	2 b Fasting	3 c Fasting	4 c,d Fasting	5 c,d,e Non-fasting	6 c,d,e Fasting	7 c,d,e Fasting	8 c,d,e Fasting	9 Fasting
Week	-6	-4	-1	0	1	4	12	24	27
Day	-42 to -29	-28	-7	1	8	29	85	169	190
Visit Window		± 3	± 3	± 0	± 5	± 5	± 5	± 5	± 5
Signed and Dated Informed consent f	X								
Inclusion/Exclusion Criteria	X	X		X g,h					
Allocation of E-code via IVRS/IWRS	X								
Randomization to study treatment via IVRS/IWRS				X					
Demographics	X								
Medical and Surgical History	X								
Brief Physical Examination i	X			X		X	X		X
Complete Physical Examination j		X						X	
Height	X								
Weight	X	X	X	X	X	X	X	X	X
CCI				X	X	X	X	X	X

Study Period	Screening period		Lead-in period		Treatment period					Follow-up period
	Enrolment	Start of lead-in	Lead-in	Randomization	Treatment	Treatment	Treatment	End of Treatment/Discontinuation/Rescue	Follow-up	
Visit	1a Non-fasting	2b Fasting	3c Fasting	4c,d Fasting	5c,d,e Non-fasting	6c,d,e Fasting	7c,d,e Fasting	8c,d,e Fasting	9 Fasting	
Visit Number (Fasting/Non-fasting)										
Week	-6	-4	-1	0	1	4	12	24	27	
Day	-42 to -29	-28	-7	1	8	29	85	169	190	
Visit Window		± 3	± 3	± 0	± 5	± 5	± 5	± 5	± 5	
Seated BP and Pulse	X	X	X	X	X	X	X	X	X	
Orthostatic BP and Pulse				X	X	X	X	X	X	
12-lead ECG k		X								
Hepatitis Screen Panel		X								
Blood samples for Safety Laboratory Panel l		X		X		X	X	X	X	
Blood samples for HbA1c	X			X		X	X	X	X	
Blood samples for S-Creatinine (eGFR calculation)	X	X	X	X		X	X	X	X	
Blood samples for FPG				X		X	X	X	X	
Assess FPG for Rescue						X	X			
CCI		X		X				X	X	
CCI				X				X	X	
Pregnancy test m	X	X	X	X	X	X	X	X	X	

Study Period	Screening period	Lead-in period		Treatment period					Follow-up period
	Enrolment	Start of lead-in	Lead-in	Randomization	Treatment	Treatment	Treatment	End of Treatment/Discontinuation/Rescue	Follow-up
Visit	1a Non-fasting	2b Fasting	3c Fasting	4c,d Fasting	5c,d,e Non-fasting	6c,d,e Fasting	7c,d,e Fasting	8c,d,e Fasting	9 Fasting
Week	-6	-4	-1	0	1	4	12	24	27
Day	-42 to -29	-28	-7	1	8	29	85	169	190
Visit Window		± 3	± 3	± 0	± 5	± 5	± 5	± 5	± 5
Urinalysis (dipstick and spot urine collection)		X		X		X	X	X	X
Timed urine sample collection (24-hours)				X				X	
Dietary and life-style advice		X		X		X	X	X	
Dispense Glucose Meter and/or Supplies (including diaries) /Provide Instructions		X	X	X	X	X	X	X	
Review of diaries			X	X	X	X	X	X	X
Dispensation of Study Medication via IVRS/IWRS		X		X		X	X		
Return of Study Medication and accountability				X		X	X	X	
Adverse event review (AEs and SAEs) n	X	X	X	X	X	X	X	X	X
Hypoglycemic events review		X	X	X	X	X	X	X	X
Concomitant medication	X	X	X	X	X	X	X	X	X

a Screening procedures, indicated under Visit 1, can be completed over multiple visits, provided all procedures have been completed, with the results reviewed, prior to Visit 2.

- b Patients must have their Visit 2 completed within 14 days following Visit 1. Visit window of  $\pm 3$  for Visit 2 corresponds to the randomization visit (Visit 4). Note: The single-blind lead-in study medication and the central laboratory results from Visit 1 must have been received at the site prior to completing the entry into Visit 2.
- c Central Laboratory samples must be collected in a fasting state (at least 8 hours of fasting prior to the study visit) except visit 5, and patients should be seen between 6 a.m. and 10 a.m. Patients must refrain from tobacco/nicotine for 12 hours and alcohol for 24 hours, respectively prior to study visits. Ensure to collect all fasting blood samples prior to the morning dose(s) of blinded study medication. Doses of study medication and other concomitant medications on the day of the visits must be taken upon completion of study visit procedures. (See CSP, Section 3.8).  
Double-blind treatment period visits must be scheduled according to the randomization visit date (Day 1), with a protocol-allowed visit window of  $\pm 5$  days. Patients will bring their glucose meter and study supplies to the site at all visits. Any slippage in time from one visit must not accumulate to affect other visits.
- e Randomized patients discontinuing study medication or requiring rescue should have Week 24 procedures done at the time of anti-diabetic rescue or study medication discontinuation. All patients who discontinue study medication will be asked to continue ordinary visit schedule, unless they entirely withdraw consent from the study. In patients discontinuing the study due to AE/SAE, the Investigator will follow the patients until the event has resolved or stabilized.
- f The signature of the ICF by the prospective patient should be obtained at Visit 1. When only the Informed Consent is signed, and all other screening visit procedures are completed.
- g eGFR value for inclusion is based on eGFR value between 45 – 59 mL/minute/1.73 m^2 at Visit 1, or Visit 2, or Visit 3.
- h Lab values for inclusion will be based on results from Visit 2 and Visit 3. Lab values from Visit 4 will be used as baseline values for study entry.
- i A brief physical examination should include cardiovascular (CV), lungs, abdomen, and extremities; and any organ systems pertinent to the patient's signs, symptoms, or AEs.
- j A complete physical examination should include general appearance, head, eyes, ears, nose, throat, neck, CV, lungs, abdomen, lymph nodes, extremities, neurological, skin, and musculoskeletal.
- k The 12-lead ECG must be performed at Visit 2. The results from this ECG must be available, assessed, and initialed and dated by the Investigator prior to Visit 4.
- l Includes Hematology and Clinical chemistry. Please refer to CSP, Section 5.2.1, Table 3.
- m Only for WOCBP. Blood sample will be collected for serum  $\beta$ HCG test, only if urine test is positive.
- n SAEs will be collected from the time of informed consent and AEs will be collected from the start of the placebo lead-in (Visit 2).

### Screening Period (V1 to V2, 2 weeks)

At Visit 1, all potentially eligible patients will provide informed consent, undergo screening for HbA1c, eGFR level and other applicable inclusion/exclusion criteria. Visit 1 can be completed over multiple visits, provided all procedures have been completed, with the results reviewed, prior to Visit 2. Patients at risk for volume depletion due to co-existing conditions or concomitant medications, such as loop diuretics, should have careful monitoring of their volume status.

### Placebo Lead-in Period (V2 to V4, 4 weeks)

At Visit 2 (start of lead-in), patients will be examined for HbA1c, and eGFR level, from blood sample obtained from Visit 1. If the HbA1c is  $\geq 7.0\%$  and  $\leq 11\%$  and the eGFR value is within the range of 40-65 mL/min/1.73 m^2 (MDRD-formula), patients will enter a 4-week single-blind placebo lead-in period. Blood samples will be collected for standard lab values (and eGFR level).

At Visit 2 and Visit 3, eGFR will be measured.

At Visit 4, patients who meet all of the inclusion and none of the exclusion criteria, the eGFR value within the range of 45-59 mL/min/1.73 m^2 at Visit 1, or Visit 2, or Visit 3, and the standard lab values (from Visit 2) will be randomized to the 24-week double-blind treatment period.

**Table 3 Summary of the algorithm for inclusion based on HbA1c and eGFR**

Visit	Algorithm
Sample obtained at Visit 1:	HbA1c $\geq 7.0\%$ and $\leq 11\%$
	eGFR 40-65 mL/min/1.73 m  , MDRD-formula
Samples obtained at Visit 1, or Visit 2, or Visit 3:	eGFR 45-59 mL/min/1.73 m  , MDRD-formula

At randomization, patients will be stratified according to pre-enrolment anti-hyperglycemic therapy. The 5 strata are listed in Section 1.3.

